7.6 Missing data

(ICH E3; 9.7.1, 11.4.2.2. ICH E9;5.3. EMA Guideline on Missing Data in Confirmatory Clinical Trials)

We will report the number of missing values for each endpoint. Patients with missing values in the primary analysis and clinical response outcomes (cORR, ORR and DCR) will be considered non-responders. The analysis of time-dependent secondary endpoints (progressions, treatment failures and deaths) will be based on a log-rank test or on Cox regression tests and therefore, will not be affected by the withdrawal of patients (as they would be censored), provided that withdrawals are not related to the prognosis. Patients with missing data regarding endpoints, such as objective response, will be considered patients with no response to treatment. In addition, we will also report the reasons for withdrawal for each allocated patient.

7.7 Multi-centre studies

(ICH E3; 9.7.1, 11.4.2.4. ICH E9; 3.2)

Individual centre results will be analysed combined in a single cohort. In accordance with previous experiences we assume that the center will not have relevant effect on safety or the activity of the study treatment.

7.8 Multiple testing

(ICH E3; 9.7.1, 11.4.2.5. ICH E9; 2.2.5)

All efficacy analyses will be exploratory. Positive results in this trial has not a confirmatory meaning, however, they will indicate that osimertinib (AZD9291) might be considered in the supportive tests. However the statistical design was based on a superiority binomial test of ORR. The statistical test has 90% power to detect a 20% increase over 50% ORR observed with other strategies in previous studies. The total type I error was adjusted in accordance with the stopping boundaries constraints in a Simon Two-stage design. The design yields a type I error rate of 0.025.

All secondary efficacy analysis has been considered supportive of primary endpoint and we have not planned a formal correction of the alpha error due to multiple testing.

Subgroup analysis has been considered exploratory, too. However, multiplicity issues derived from analysing multiple hypothesis will be adjusted by the Q-value index at 10% nominal level, based on (Storey JD, Bass AJ, Dabney A and Robinson D (2018). qvalue: Q-value estimation for false discovery rate control. R package version 2.14.0, <http://github.com/jdstorey/qvalue>).

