6.3 Study population

(ICH E3;9.3. ICH E9;2.2.1)

Patients diagnosed with stage IIIB or IV non-small cell lung cancer carrying the EGFR activating mutation and confirming concomitant T790M mutation during screening who have not received prior treatment for this advanced disease will be enrolled in this study. Patients are not eligible if they are candidates for local curative treatment.

The analysis of EGFR mutational status (del19, L858R, L861Q or G719X) may be previously performed at each of the participating sites, but the tumor material taken from all patients should be submitted to the central laboratory for supportive analysis and T790M mutation analysis.

The patient's signed informed consent should be obtained before sending the tumor tissue sample to the central laboratory.

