7.5 Covariates and subgroups

(ICH E3; 9.7.1, 11.4.2.1. ICH E9; 5.7. CPMP 2002; 4.CPMP 2003.)

Difference between baseline tumor measurements and those observed throughout the study will be analyzed using the Wilcoxon test. Patients with and without different types of EGFR mutation will be compared. For binary outcomes (cORR, ORR and DCR), the chi-square or Fisher's exact test will be used. For time objectives (PFS, OS, TTF and DOR), the Kaplan-Meier method and log-rank test will be used. For continuous objectives (percentage of Tumor Shrinkage, TS), the Mann-Whitney U test will be used.

Baseline biomarker levels will be correlated with the clinical response. For binary and continuous results, the Spearman correlation will be used. For time objectives (PFS), the Kaplan-Meier method and log-rank test will be used. The categorization or log-transformation of biomarker levels will be considered.

The feasibility of re-biopsies at the time of progression will be estimated with the number and percentage of patients with rebiopsy and 95% confidence interval.

The presence of mutations and biomarker levels (tissue or blood) will be compared from baseline to time of progression with the Mc Nemar and Wilcoxon tests, respectively.

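### The 10% false-discovery level set for the exploratory subgroup tests is not assured by a q-value that estimates the null share from about 8 to 32 tests

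*SAP*

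**What the plan says.** SAP 7.8 states that "Subgroup analysis has been considered exploratory, too", and adds that "multiplicity issues derived from analysing multiple hypothesis will be adjusted by the Q-value index at 10% nominal level". The tool cited is "qvalue: Q-value estimation for false discovery rate control. R package version 2.14.0". The section does not say which tests form the family, how many there are, how the null share is estimated, or what happens if that estimate fails.

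The tests are described in SAP 7.5: "Patients with and without different types of EGFR mutation will be compared". Three kinds of endpoint are then tested:

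- three binary endpoints (confirmed response, response without confirmation, and disease control), by a chi-square or Fisher test;
- four time-to-event endpoints: "For time objectives (PFS, OS, TTF and DOR), the Kaplan-Meier method and log-rank test will be used";
- one continuous endpoint, tumor shrinkage, by a Mann-Whitney test.

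SAP 6.3 names four mutation types. SAP 7.5 also describes baseline biomarker correlations, biomarker log-rank tests and comparisons from baseline to progression. SAP 7.8 does not say whether these belong to the adjusted family.

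**The concern.** A Storey q-value is the Benjamini-Hochberg adjusted p-value multiplied by an estimate of the share of true nulls. That estimate comes from how many p-values lie in the upper part of the unit interval. With hundreds of tests it is stable. With 8 to 32 it is noisy and is normally capped at 1, so its errors run mainly one way: a low estimate shrinks every q-value, and a high one cannot compensate. The spline form can also return zero or a negative number, and the analyst would then have to choose a fallback after seeing the p-values.

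At stake is the meaning of the 10% attached to any subgroup finding. SAP 7.8 plans no correction for the secondary analyses, so this is the only multiplicity control it offers beyond the primary test.

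**Working it through.** **Inputs.** Nominal level 10% (SAP 7.8). Endpoints per contrast: 3 binary + 4 time-to-event + 1 continuous = 8 (SAP 7.5). Mutation types: 4 (SAP 6.3). Family size m by counting: 8 × 1 = 8 to 8 × 4 = 32. This range is an inference. Planned n is 73 (SAP 6.4). SAP 9 says accrual was closed after the interim review, so n of about 21 is also considered, as an assumption.

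**Rule.** Flag a test if q ≤ 0.10, which is Benjamini-Hochberg run at 0.10/π̂, where π̂ is the estimated null share. If all nulls are true, every flag is false, so the false-discovery rate is the chance of at least one flag.

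**Hand check, 8 independent true nulls, lambda fixed at 0.5.** Let W be the number of p-values above 0.5, so π̂ = min(1, W/4). The other 8 − W are uniform on (0, 0.5). By the Simes identity, for W of 1 or more, the chance of a flag given W is 2 × (8 − W)/8 × 0.10/π̂.

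| W | Probability | π̂ | Level in effect | Chance of a flag | Product |
|---|---|---|---|---|---|
| 0 | 1/256 | 0 | none | 1 (all q = 0) | 0.0039 |
| 1 | 8/256 | 0.25 | 0.40 | 0.700 | 0.0219 |
| 2 | 28/256 | 0.50 | 0.20 | 0.300 | 0.0328 |
| 3 | 56/256 | 0.75 | 0.133 | 0.167 | 0.0365 |
| 4 | 70/256 | 1 | 0.10 | 0.100 | 0.0273 |
| 5 | 56/256 | 1 | 0.10 | 0.075 | 0.0164 |
| 6 | 28/256 | 1 | 0.10 | 0.050 | 0.0055 |
| 7 | 8/256 | 1 | 0.10 | 0.025 | 0.0008 |
| 8 | 1/256 | 1 | 0.10 | 0 | 0 |

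The sum is 0.145; simulation gave 0.147. With π̂ fixed at 1 the same formula averages to 2 × 0.10 × 4/8 = 0.10. So the plan's 10% is reproduced when the null share is not estimated, and the excess comes from the rows with W below 4.

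**Simulation, independent true nulls.** The spline is a cubic smoothing spline with 3 degrees of freedom over lambda 0.05 to 0.95.

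| Tests | Null share fixed at 1 | Lambda 0.5 | Bootstrap lambda* | Spline, all runs | Spline: no usable estimate |
|---|---|---|---|---|---|
| 8 | 10% | 15% | 9% | about 22% | 15% |
| 16 | 10% | 12% | 12% | about 20% | 4% |
| 24 | 10% | not run | not run | about 18% | 1% |
| 32 | 10% | 11% | 13% | about 16% | 0.4% |

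*An estimate of zero is counted as no flag.

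At 8 tests the spline figure is 21-23% over all runs, depending on the fallback when the estimate fails, and 25% among runs that return an estimate. With larger families it falls to 14% at 50 tests, 12% at 100 and 10% at 500. With 8 tests of which 25% are true effects (shift 3 SD), the spline gives 17-19% and Benjamini-Hochberg 7.6%.

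**Correlated nulls, 8 tests, spline.** The level is 19-22% at correlation 0.3. At 0.7 it is about 8-9% if a failed estimate counts as no flag (higher if the analyst falls back to a null share of 1). At 0.9 it is 3-9% across those two fallbacks.

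**Trial-like null data.** The eight endpoints were generated with shared patient-level correlation, response about 70%, median PFS 12 months and 18 months of follow-up (all assumed), then analysed with Fisher, log-rank and Mann-Whitney tests.

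| Tests, n (group sizes) | Null share 1 | Lambda 0.5 | Bootstrap | Spline |
|---|---|---|---|---|
| 8, n = 73 (37/36) | 8% | 15% | 7% | 13-16% |
| 8, n = 21 (11/10) | 7% | 13% | 7% | 8-11% |
| 32, n = 73 (28/31/7/7) | 10.9% | 12.5% | not run | 12.1% |
| 32, n = 21 (8/9/2/2) | 20.5% | 21.8% | not run | 20.5% |

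In the last row the null-share setting makes almost no difference. The likely cause is asymptotic log-rank p-values in groups of two patients.

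**The case against.** The documents state no number of tests. If the biomarker tests in SAP 7.5 join the family, it is larger, and SAP 5.2.3 leaves the list of biomarkers open. Nor do the documents name the spline, and the bootstrap variant is much milder. A null share of 1 is itself one setting of the q-value, so the gap can be read as an unspecified option. The real endpoints overlap heavily and the binary ones may use conservative Fisher tests; at about 21 patients the spline level is then close to 10%. Finally, all efficacy analyses are declared exploratory, and SAP 7.10 rests a positive study on the primary test alone.

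Most of this stands and limits the point. A reader might infer that the q-value never delivers 10% here, or that the true level is 25%. The documents support neither: the level depends on settings, correlation and sample size that the SAP leaves open, and the 25% excludes runs with no estimate. What remains is that the same SAP sentence permits levels from below 10% to about 23% with independent tests, and higher still if every test were flagged when the estimate fails (30% in the trial-like data at n = 73). Nothing in the documents points to the hundreds of tests at which the estimate settles. The exploratory label lowers the consequence but does not make the stated 10% accurate.

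**Conclusion.** The concern holds in a limited form: 10% is not assured for a family as small as SAP 7.5 implies. Under independent true nulls the spline setting gives about 16-22% for 8 to 32 tests and lambda 0.5 about 11-15%. In trial-like null data with 8 tests the spline gives about 13-16% at the planned 73 patients and about 8-11% at about 21. These figures rest on an inferred family size, an assumed estimator and assumed endpoint behaviour. There is also no rule for a failed estimate, which occurs in about 15% of independent 8-test families. The consequence is small: the labelling of exploratory subgroup findings is affected, and the primary test and its decision rule are not.

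**What to change.** In SAP 7.8, replace the q-value with an estimated null share by the Benjamini-Hochberg procedure at 10% (null share fixed at 1). List the family it applies to: each mutation contrast and endpoint, and whether the biomarker tests are included. This removes both the excess from estimating the null share and the need for a fallback.

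The 10% then holds only where the p-values themselves are valid. For log-rank comparisons in mutation groups of a few patients, add that exact or permutation p-values will be used, or that results will be descriptive only. Changing the false-discovery method would not cure the 20.5% seen with groups of two.

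The cost is one amended sentence, a short list of tests and slightly fewer flagged subgroup findings. No added data or change to the primary analysis is needed.

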7.9 Interim analyses and data monitoring

(ICH E3; 9.7.1, 11.4.2.3. ICH E9; 4.1, FDA Feb 2010 “Guidance for Industry Adaptive Design Clinical Trials for Drugs and Biologics”)

7.9.1 Purpose of interim analyses

We have planned an interim analysis to reduce the number of patients exposed if the therapeutic regimen investigated was inefficient or unsafe. We propose an interim analysis with a futility boundary, but not with efficacy boundary. The study will be only finished for primary outcome if the results are not promising. We do not want to stop the trial early for efficacy because we will recruit only a few patients at interim (21). The early discontinuation of the trial will impact negatively in the power of primary and secondary analysis if the combination is promising. However, the decision to stop and continue the trial should be agreed by the steering committee after reviewing the interim safety and efficacy data.

7.9.1 Stopping rules

The efficacy and safety results of the interim analysis will be evaluated by a Scientific Committee that will decide on the suitability of continuing with the study. The study will only be interrupted in case of futility (if there are 11 or fewer responses in these 21 patients) or safety (in case of any arising safety concern after steering committee review).

7.10 Decision rules and adjustment of alpha for primary endpoint at final analysis

The study will be declared positive if the following outcome are achieved:

1. Final analysis: The p-value estimated according stochastic ordering of uniformly minimum variance unbiased estimator (UMVUE) is <0.025 . According with these criteria, if 73 patients are included in the analysis we will achieve a positive finding with 45 or more responders.

7.11 Steering committee review

A Scientific Committee (SC) has been appointed for this study. Initially, the committee consists of the investigators, the study Medical Monitor and two physicians specialized in osimertinib (AZD9291) therapy.

The SC will meet on demand to review, discuss and evaluate all of the collected safety data. In the event of a safety issue, a meeting can also be called at any time at the request of an investigator participating in the study. At these meetings, MedSIR ARO and the participating investigators must reach a consensus on safety data. MedSIR ARO will prepare minutes for these meetings and submit them to each investigator for comment prior to finalization.

The study site Investigators and MedSIR ARO will review patient data at least every four months. Each study site investigator will regularly review patient data to detect serious side effects.

7.11.1 Adjustment of confidence intervals and p-values

The total type I error was adjusted in accordance with the stopping boundaries constraints in a Simon Two-stage design. The design yields a type I error rate of 0.025.

We account for the sequential nature of the design calculating the responder rate, confidence interval and p-values of primary endpoint in accordance with UMVUE method. The equation has been described in primary endpoint section.

7.11.2 Practical measures to minimize bias

This is an open label study with a descriptive purpose. All efficacy analyses will be exploratory. Positive results in this trial has not a confirmatory meaning. In accordance, the interim and final analysis will not be developed by different teams of statisticians. The decisions at interim analysis will be made by the steering committee and they will decide the information that will be publically available following the interim analysis.

7.11.3 Documentation of interim analyses

Snapshots of the data available at each interim analysis should be preserved, as should all documentation of analysis plans, programming code and reporting provided at each interim. It should be possible to recreate the decision process from the trial archive. Record what documents will be created and stored thus.

7.12 Reporting conventions

7.12.1 General reporting conventions

All tables, figures and data listings will be presented in portrait orientation, unless landscape orientation suggests that the information is easier to view. Legends will be used for all figures with more than one variable or item displayed. Figure lines should be wide enough to see the line after being copied.

Titles of all tables, listings and figures should contain the following information:

- Output number.
- Description of the data that is being summarized.
- Type of analysis performed, covariates used (if applicable).
- Analysis population.

7.12.2 Statistical summary conventions

For tables, sample sizes for each treatment group will be presented as totals in the column header (N=xxx), where appropriate. Sample sizes shown with summary statistics are the number (n) of patients with non-missing values.

Summaries for categorical variables will include only categories that patients had a response in. Percentages corresponding to null categories (cells) will be suppressed. All summaries for continuous variables will include: N, mean, and SD. Other summaries (e.g. median, quartiles, 5%, 95% intervals, range or interquartile range) will be used as appropriate. All percentages should be rounded and reported to a single decimal place (xx.x%). If percentages are reported as integers, percentages greater than 0% but <1% will be reported as <1%, whereas percentages greater than 99% but <100% will be reported as >99%. A percentage of 100% will be reported as 100%. No value of 0% should be reported. Any computation of percent that results in 0% is to be reported as a blank. P-values will be reported with three decimal places with a leading zero (0.001). P-values <0.001 will be reported as <0.001.

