6.9.1 Dose reduction

In the event of a significant treatment-related side effect, the osimertinib (AZD9291) dose can be interrupted, delayed and/or reduced, as described below. In the event of multiple side effects, dose change should be based on the worst toxicity observed. Patients are instructed to notify the investigator the moment he/she notices any adverse signs or symptoms.

After an interruption in administration or a delay in a cycle, a dose reduction may be necessary when treatment is to be resumed. No specific dose adjustments are recommended for Grade 1 or 2 treatment-related toxicity.

However, investigators should always use their judgment when treating patients, in accordance with the specific clinical circumstances. A reduction in osimertinib (AZD9291) dose by 1 dose level (Table 2) is permitted, based on the type and severity of the side effect. Patients requiring more than 1 dose reductions will be discontinued from the study and entered into the follow-up phase. All dose changes/adjustments should be clearly noted in the original patient record and in the CRF.

Table 2. Osimertinib (AZD9291) dose reduction

Dosing level	Osimertinib (AZD9291) for 3 weeks
Starting dose	80 mg/day
- 1	40 mg/day
	Discontinue study treatment

Table 3. Osimertinib (AZD9291) dose adjustment after adverse reactions

Organ involved	Adverse Reaction	Dose change
Lung	ILD/Pneumonia	Discontinue the treatment . permanently.
Heart	QTc interval >500 ms at least in 2 different ECGs.	Maintain of osimertinib (AZD9291) until the QTc interval <481 ms or go back to baseline results if they are ≤481 ms and then, restart at a reduced dose (40 mg).
	QTc interval prolongation with signs/symptoms of severe arrhythmia.	Discontinue osimertinib (AZD9291) permanently.
Other	Grade 3 or higher adverse reaction.	Discontinue osimertinib (AZD9291) up to 3 weeks.

EudraCT No.: 2015-004828-66 Protocol No.: MedOPP112 Protocol date: May 21, 2018

Version 3

If the grade 3 adverse reaction improves to grade 2 or lower after osimertinib discontinuation up to 3 weeks	The administration of osimertinib (AZD9291) may start at a normal dose (80 mg) or at a reduced dose (40 mg).
If the grade 3 adverse reaction improves to grade 2 or lower after osimertinib discontinuation up to 3 weeks.	Discontinue osimertinib (AZD9291) permanently.

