6.9.2 Interruption of administration

The dose may be interrupted, when necessary, until the resolution of toxicity. Depending on when the adverse event is resolved, an interruption in therapy may cause the patient to miss subsequent doses that have been scheduled for that cycle and even delay the start of the next cycle.

Administration of osimertinib (AZD9291) should be permanently discontinued under the following circumstances:

- Interstitial pneumonitis.
- Hepatic insufficiency.
- Gastrointestinal perforation.
- Corrected QT interval prolongation with signs/symptoms of severe arrhythmia.
- Suspension of treatment lasting more than 3 weeks.

If the adverse event that gave rise to the interruption of treatment is resolved within that same cycle, the treatment can be resumed in that cycle. Doses not administered due to toxicity will not be replaced in that same cycle. The need for a dose reduction when treatment is to be resumed should be assessed in keeping with the criteria defined above, unless otherwise agreed upon by the investigator and sponsor. If a dose reduction is made within the cycle, the patient should come to the site to receive a new supply of the drug. If the treatment is interrupted for reasons other than treatment-related toxicity (e.g., surgery not related to cancer) for a period >2 weeks, treatment can only be resumed after consultation with the sponsor.

The appropriate follow-up assessments should be performed until adequate resolution has been reached, in the judgment of the investigator. If these parameters are not met within 3 weeks after the dose interruption (including the scheduled treatment week during which the patient did not receive treatment), then the treatment should be considered permanently discontinued. Treatment can be resumed in cases where patients have recovered from a treatment-related side effect after a period in which treatment has been discontinued for more than 3 weeks or after the cycle has been delayed, but only if treatment offers a clinical benefit to the patient in the judgment of the investigator. In these cases, it is left to the discretion of the investigator after consultation with the sponsor.

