This data suggests that excluding an ORR $\leq 50\%$ while targeting the improvement of the ORR to $\geq 70\%$ would be a conservative approach to assess the osimertinib (AZD9291) treatment effect in this patient population. Accordingly, this study will test the null hypothesis that the ORR is $\leq 50\%$ against the alternative hypothesis that it is $\geq 70\%$. Applying Simon's optimum 2-stage design (Simon, R 1989), a sample size of 73 patients has power > 0.90 to achieve a 1-sided significance level of 0.025. In the first stage, 21 patients will be accrued. If there are 11 or fewer responses in these 21 patients, the study will be stopped. Otherwise, 52 additional patients will be accrued for a total of 73 patients. The null hypothesis will be rejected if 45 or more responses are observed in 73 patients. This design yields a type I error rate of 0.025 and a power of 90% when the ORR is 70%. The recruitment will be competitive between sites.

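### SAP 7.12.2 drops empty categories and blanks 0% in summary tables, so a planned result of zero may look the same as one that was not assessed

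*SAP*

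**What the plan says.** SAP 7.12.2 sets conventions for summaries in general. "Summaries for categorical variables will include only categories that patients had a response in". "Percentages corresponding to null categories (cells) will be suppressed". It then bars any value of 0% and closes with "Any computation of percent that results in 0% is to be reported as a blank". The column-header N is kept, and the sample size shown beside a summary statistic is the number of patients with non-missing values. No exception is made for safety or efficacy tables.

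Other sections plan results that can be zero:

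- SAP 7.2 undertakes to give the number and percentage of patients with CR, PR, SD and progression.
- SAP 5.2.3 lists, as an endpoint, the percentage of patients with C797 or other mutations.
- SAP 7.3 plans to describe exposure, clinically relevant tests, reported adverse events, serious adverse events, deaths and discontinuations. It names no individual harm and plans no interval for any harm rate.

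The protocol does name harms. Table 3 in section 6.9.1 has rows for ILD/pneumonia and for "QTc interval >500 ms at least in 2 different ECGs". Section 6.9.2 lists interstitial pneumonitis, hepatic insufficiency, gastrointestinal perforation and "Corrected QT interval prolongation with signs/symptoms of severe arrhythmia". Protocol 5.2 schedules ECGs every 12 weeks.

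**The concern.** In a small single-arm trial, zero is a result. It can be interpreted only as 0 out of a stated number assessed, preferably with an upper limit. A missing row or a blank cell can mean that nobody had the outcome, that nobody was tested, or that the item was not analysed.

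Safety and tolerability is a secondary objective, and toxicity is part of the first interim report that goes to the committee (SAP 6.6). For C797 the number tested may be well below the header N, because Protocol 5.2 makes re-biopsy at progression a recommendation only. What is at stake is whether a reader of the tables can interpret a null finding. No estimate or decision rule is involved.

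**Working it through.** **1. Sample sizes.** SAP 6.4 gives both: "In the first stage, 21 patients will be accrued" and "Otherwise, 52 additional patients will be accrued for a total of 73 patients". The documents give no figure for a zero count, so the design that produces these sizes is the figure to reproduce. With stage 1 X1 ~ Bin(21, p) and stage 2 X2 ~ Bin(52, p), the probability of rejecting is the sum over x1 = 12 to 21 of P(X1 = x1) × P(X2 ≥ 45 − x1).

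- p = 0.50: 0.0249 (stated 0.025)
- p = 0.70: 0.9004 (stated 90%)

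Both agree, so 21 and 73 are sound inputs.

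**2. Could a blank come from rounding?** The smallest non-zero percentage is 1/21 = 4.8% or 1/73 = 1.4%. At these sizes neither can round to 0%, so blanking removes only true zeros.

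**3. What a zero is compatible with.** The exact (Clopper-Pearson) two-sided 95% upper limit for 0 of n is 1 − 0.025^(1/n). The one-sided 95% limit is 1 − 0.05^(1/n). The SAP specifies Clopper-Pearson for response only (7.1); using it for harms is an assumption here.

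| Result | Two-sided 95% upper limit | One-sided 95% upper limit |
|---|---|---|
| 0/21 | 16.1% | 13.3% |
| 0/73 | 4.9% | 4.0% |

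**4. How often a zero would arise.** P(no events) = (1 − p)^n, for an assumed range of true rates:

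| True rate p | n = 21 | n = 73 |
|---|---|---|
| 2% | 65% | 23% |
| 3% | 53% | 11% |
| 5% | 34% | 2% |
| 10% | 11% | <0.1% |

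These are properties of the sample size, not of the reporting rule. They show how often the rule would come into play.

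**5. The rule applied to each kind of result.**

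| Result of zero | Where it is planned or named | Effect of 7.12.2 | Is printing zeros enough? |
|---|---|---|---|
| CR | SAP 7.2, number and percentage promised | Row dropped; conflicts with 7.2 | Yes |
| C797 mutation | SAP 5.2.3, percentage endpoint | Category dropped or blank; conflicts with 5.2.3 | Yes, if the number tested is shown |
| QTc >500 ms | Protocol Table 3; no SAP table planned | Dropped if tabulated as a category | Only if the category is pre-listed |
| ILD, hepatic insufficiency, gastrointestinal perforation, QTc prolongation with severe arrhythmia | Protocol 6.9.1 and 6.9.2; SAP 7.3 covers reported events | No row, because nothing was reported | No; the harm must be pre-listed |

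There are thus two separate causes. For planned categories it is the zero rule. For adverse-event terms it is also the absence of any pre-listed harm in SAP 7.3.

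**The case against.** The case on the other side is substantial.

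- SAP 7.12.2 is a layout convention. It does not stop the report from stating in its text or listings that no case of ILD occurred. This stands. A reader might infer that an unseen harm goes unreported altogether; the documents do not support that.
- 16.1% is a confidence limit. A reader might infer that the rule hides a rate of up to 16%. It does not: nothing observed is concealed, and since no interval is planned for any harm, the rule removes none. The figure also assumes n = 21, whereas the planned total is 73. SAP section 9 says accrual closed after the interim review but does not give the number treated. This stands.
- QTc may be summarised as a continuous variable with its own n. If the range is given, the maximum would show whether anyone exceeded 500 ms. This is possible but not assured: 7.3 does not name QTc, and 7.12.2 asks for the range only where appropriate.
- The non-missing n, and the count of missing values for each endpoint (SAP 7.6), can separate zero from missing. A zero in the response table can also be recovered if the remaining rows add up to N. This helps for response. It does not help for adverse-event terms, which carry no n of their own.
- SAP 7.2 is the more specific text and could be read as overriding 7.12.2 for the CR row. Neither section says so, so the conflict remains to be resolved.
- Sections 6.9.1 and 6.9.2 of the protocol are dose-change and discontinuation rules, not a list of safety endpoints. This is correct; using them as a reporting list is a proposal of this review.

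**Conclusion.** The point holds as a reporting defect. SAP 7.12.2 is an explicit rule without exception. It contradicts the response summary in SAP 7.2 and the mutation percentage in SAP 5.2.3, and it can leave the reader of a table unable to tell a null result from an unassessed one. For adverse events the rule is only part of the cause, since SAP 7.3 pre-lists no harm.

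The limits in step 3 measure how much uncertainty an unprinted zero carries. They rest on complete assessment of 21 or 73 patients and on an exact interval that the SAP does not plan for harms. Fewer patients assessed would give a wider limit. The primary analysis, the design error rates and the interim stopping rule are unaffected.

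**What to change.** In SAP 7.12.2, replace the zero rule with wording such as:

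> Zero counts are reported as 0 (0.0%) with the number assessed; a blank is used only for not assessed. The CR, PR, SD, PD and NE rows and the planned mutation categories are always printed.

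In SAP 7.3, pre-list the harms that the protocol already names: ILD/pneumonitis, QTc >500 ms, QTc prolongation with severe arrhythmia, hepatic insufficiency and gastrointestinal perforation. Show n/N with an exact Clopper-Pearson 95% CI for each, including when n = 0. With 21 patients assessed, an empty row would then read 0/21 (0.0%; 95% CI 0.0% to 16.1%). Protocol Table 3 and section 6.9.2 use different terms for the lung event, so the list should state which reported terms count towards that row.

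The cost is a few sentences in the SAP and slightly longer tables. No new data are needed, and no dose or clinical rule changes.
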